- Initiate anticoagulation therapy.
- For guidelines on treatment holds, timing for restarting treatment or discontinuing treatment permanently, see Section 6.2.1, Table 2.

Gastrointestinal Perforation or Fistula Formation

- Initiate treatment according to established guidelines.
- For guidelines on treatment holds, timing for restarting treatment or discontinuing treatment permanently, see Section 6.2.1, Table 2.

Bleeding

- Initiate treatment according to established guidelines.
- For guidelines on treatment holds, timing for restarting treatment or discontinuing treatment permanently, see Section 6.2.1, Table 2.

Hepatic Encephalopathy or Other Serious Signs of Liver Impairment

- Initiate treatment according to established guidelines.
- For guidelines on treatment holds, timing for restarting treatment or discontinuing treatment permanently, see Section 6.2.1, Table 2.

5.4.2. Suggested supportive care measures for the management of adverse events that are related to nivolumab

Immuno-oncology (I-O) agents are associated with AEs that can differ in severity and duration than AEs caused by other therapeutic classes. Nivolumab is considered an immuno-oncology agent in this protocol. Early recognition and management of AEs associated with immuno-oncology agents may mitigate severe toxicity. Management algorithms have been developed to assist investigators in assessing and managing the following groups of AEs: Gastrointestinal, Renal, Pulmonary, Hepatic, Endocrinopathies, Skin, Neurological.

For subjects expected to require more than 4 weeks of corticosteroids or other immunosuppressants to manage an AE, consider recommendations provided in the algorithms. These algorithms are found in the Nivolumab IB and in Appendix 1. The guidance provided in these algorithms should not replace the Investigator's medical judgment but should complement it.

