6.3.2 Nivolumab Dose Delay Criteria

Adverse events (both non-serious and serious) associated with nivolumab exposure may represent an immunologic etiology. These adverse events may occur shortly after the first dose or several months after the last dose of treatment. Nivolumab must be withheld for drug-related toxicities and severe or life-threatening AEs as per Table 3 below. See Section 5.4 for supportive care guidelines, including use of corticosteroids. **NOTE:** In addition to information in the table, permanently discontinue for any severe or Grade 3 drug-related AE that recurs or any life-threatening event. Subjects with intolerable or persistent Grade 2 drug-related AE may have study medication held at physician discretion. Permanently discontinue study drug for persistent Grade 2 adverse reactions for which treatment with study drug has been held, that do not recover to Grade 0-1 within 6 weeks of the last dose unless delay beyond 6 weeks allows for prolonged steroid taper to manage toxicity. In such cases, the Sponsor Investigator must be consulted prior to re-initiating treatment.

Table 3: Nivolumab dose modification guidelines for drug-related adverse events

Toxicity	Hold Treatment For	Timing for Restarting Treatment	Discontinue Subject
Diarrhea/Colitis	Grade 2-3	Toxicity resolves to Grade 0-1	Toxicity does not resolve within 6 weeks of last dose unless delay beyond 6 weeks allows for prolonged steroid taper to manage toxicity. In such cases, the Sponsor Investigator must be consulted prior to re-initiating treatment.
	Grade 4	Permanently discontinue	Permanently discontinue
Pneumonitis	Grade 2	Toxicity resolves to Grade 0-1	Toxicity does not resolve within 6 weeks of last dose unless delay beyond 6 weeks allows for prolonged steroid taper to manage toxicity. In such cases, the Sponsor Investigator must be consulted prior to re-initiating treatment.
	Grade 3-4	Permanently discontinue	Permanently discontinue
Hepatitis	≥ Grade 2 if subject has baseline AST, ALT or total bilirubin that is within normal limits; ≥ Grade 3 if subject has baseline AST, ALT or total bilirubin within the Grade 1 toxicity range	Toxicity resolves to Grade 0-1	Toxicity does not resolve within 6 weeks of last dose unless delay beyond 6 weeks allows for prolonged steroid taper to manage toxicity. In such cases, the Sponsor Investigator must be consulted prior to re-initiating treatment.

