	AST or ALT > 8 x ULN OR total bilirubin >5 x ULN OR concurrent AST or ALT > 3 x ULN and total bilirubin > 2 x ULN	Permanently discontinue	Permanently discontinue
Type I diabetes mellitus [T1DM] (if new onset) or Hyperglycemia	New onset T1DM or Grade 3 hyperglycemia	Toxicity resolves to Grade 0-1 even if requires physiologic hormone replacement	Resume nivolumab when subjects are clinically and metabolically stable.
	Grade 4	May need to permanently discontinue; see footnote #4	May need to permanently discontinue; see footnote #4
Hypophysitis	Grade 2-3	Toxicity resolves to Grade 0-1	Toxicity does not resolve within 6 weeks of last dose unless delay beyond 6 weeks allows for prolonged steroid taper to manage toxicity. In such cases, the Sponsor Investigator must be consulted prior to re-initiating treatment.

Toxicity	Hold Treatment For	Timing for Restarting Treatment	Discontinue Subject
	Grade 4	Permanently discontinue	Permanently discontinue
Nephritis and Renal Dysfunction	Serum creatinine more than 1.5 and up to 6 times the upper limit of normal	Toxicity resolves to Grade 0-1	Toxicity does not resolve within 6 weeks of last dose unless delay beyond 6 weeks allows for prolonged steroid taper to manage toxicity. In such cases, the Sponsor Investigator must be consulted prior to re-initiating treatment.
	Serum creatinine more than 6 times the upper limit of normal	Permanently discontinue	Permanently discontinue
Skin	Grade 3 rash or suspected Stevens-Johnson syndrome (SJS) or toxic epidermal necrolysis (TEN)	Toxicity resolves to Grade 0-1	Toxicity does not resolve within 6 weeks of last dose unless delay beyond 6 weeks allows for prolonged steroid taper to manage toxicity. In such cases, the Sponsor Investigator must be consulted prior to re-initiating treatment.
	Grade 4 or confirmed SJS or TEN	Permanently discontinue	Permanently discontinue
Encephalitis	New-onset moderate or severe neurologic signs or symptoms	Toxicity resolves to Grade 0-1	Toxicity does not resolve within 6 weeks of last dose unless delay beyond 6 weeks allows for prolonged steroid taper to manage toxicity. In such cases, the Sponsor Investigator must be consulted prior to re-initiating treatment.
	Immune-mediated encephalitis	Permanently discontinue	Permanently discontinue
Adrenal Insufficiency	Grade 2	Toxicity resolves to Grade 0-1 even if requires physiologic hormone replacement	Toxicity does not resolve within 12 weeks of last dose.

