
17 APPENDIX 1: Nivolumab Management Algorithms

These general guidelines constitute guidance to the site Investigator and may be supplemented through discussions with the Sponsor-Investigator by contacting the HCRN project manager. The guidance applies to all immuno-oncology agents and regimens.

As general principle, differential diagnoses should be diligently evaluated according to standard medical practice. Non-inflammatory etiologies should be considered and appropriately treated.

[figure not shown]
Corticosteroids are a primary therapy for immuno-oncology drug-related adverse events. The oral equivalent of the recommended IV doses may be considered for ambulatory patients with low-grade toxicity. The lower bioavailability of oral corticosteroids should be taken into account when switching to the equivalent dose of oral corticosteroids.

Consultation with a medical or surgical specialist, especially prior to an invasive diagnostic or therapeutic procedure, is recommended.

The frequency and severity of the related adverse events covered by these algorithms will depend on the immuno-oncology agent or regimen being used.

GI Adverse Event Management Algorithm

Rule out non-inflammatory causes. If non-inflammatory cause is identified, treat accordingly and continue I-O therapy. Opiates/narcotics may mask symptoms of perforation. Infliximab should not be used in cases of perforation or sepsis.

[figure not shown]

Patients on IV steroids may be switched to an equivalent dose of oral corticosteroids (e.g. prednisone) at start of tapering or earlier, once sustained clinical improvement is observed. Lower bioavailability of oral corticosteroids should be taken into account when switching to the equivalent dose of oral corticosteroids.

Updated 05-Jul-2016

Renal Adverse Event Management Algorithm

Rule out non-inflammatory causes. If non-inflammatory cause, treat accordingly and continue I-O therapy

[figure not shown]

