Patients on IV steroids may be switched to an equivalent dose of oral corticosteroids (e.g. prednisone) at start of tapering or earlier, once sustained clinical improvement is observed. Lower bioavailability of oral corticosteroids should be taken into account when switching to the equivalent dose of oral corticosteroids.

Updated 05-Jul-2016

Pulmonary Adverse Event Management Algorithm

Rule out non-inflammatory causes. If non-inflammatory cause, treat accordingly and continue I-O therapy. Evaluate with imaging and pulmonary consultation.

[figure not shown]

Patients on IV steroids may be switched to an equivalent dose of oral corticosteroids (e.g. prednisone) at start of tapering or earlier, once sustained clinical improvement is observed. Lower bioavailability of oral corticosteroids should be taken into account when switching to the equivalent dose of oral corticosteroids.

Updated 05-Jul-2016

Hepatic Adverse Event Management Algorithm

Rule out non-inflammatory causes. If non-inflammatory cause, treat accordingly and continue I-O therapy. Consider imaging for obstruction.

Patients on IV steroids may be switched to an equivalent dose of oral corticosteroids (e.g. prednisone) at start of tapering or earlier, once sustained clinical improvement is observed. Lower bioavailability of oral corticosteroids should be taken into account when switching to the equivalent dose of oral corticosteroids.

[figure not shown]
*I-O therapy may be delayed rather than discontinued if AST/ALT \leq 8 x ULN or T.bili \leq 5 x ULN.

**The recommended starting dose for grade 4 hepatitis is 2 mg/kg/day methylprednisolone IV.

Updated 05-Jul-2016

Endocrinopathy Management Algorithm

Rule out non-inflammatory causes. If non-inflammatory cause, treat accordingly and continue I-O therapy. Consider visual field testing, endocrinology consultation, and imaging.

[figure not shown]

Patients on IV steroids may be switched to an equivalent dose of oral corticosteroids (e.g. prednisone) at start of tapering or earlier, once sustained clinical improvement is observed. Lower bioavailability of oral corticosteroids should be taken into account when switching to the equivalent dose of oral corticosteroids.

Updated 05-Jul-2016

Skin Adverse Event Management Algorithm

Rule out non-inflammatory causes. If non-inflammatory cause, treat accordingly and continue I-O therapy.

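### Appendix 1's hepatic footnote and Table 3 conflict on delaying versus permanently stopping nivolumab, and nothing says which governs

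*Combined protocol and SAP*

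**What the plan says.** The hepatitis rows of Table 3 (Section 6.3.2) name three sets of liver values for which nivolumab is stopped for good. Two concern a single analyte: "AST or ALT > 8 x ULN OR total bilirubin >5 x ULN". The third is a combined rise at lower levels, with AST/ALT above 3 x and bilirubin above 2 x ULN at the same time. Any one of the three is enough. The table is introduced in mandatory terms: "Nivolumab must be withheld for drug-related toxicities and severe or life-threatening AEs as per Table 3 below".

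The Hepatic Adverse Event Management Algorithm in Appendix 1 carries an asterisked footnote on the same decision: "I-O therapy may be delayed rather than discontinued if AST/ALT \leq 8 x ULN or T.bili \leq 5 x ULN". It says nothing about a concurrent rise in transaminases and bilirubin at lower levels.

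The status of the Appendix is described at its start: "These general guidelines constitute guidance to the site Investigator", and "The guidance applies to all immuno-oncology agents and regimens". The body of the protocol sends readers there. Section 6.3.2 refers to Section 5.4 for supportive care, and Section 5.4.2 says of the algorithms: "These algorithms are found in the Nivolumab IB and in Appendix 1". Section 10.2.9 gives the same pointer. Section 5.4.2 adds that the algorithms complement the investigator's medical judgment and do not replace it. No sentence says whether Table 3 or Appendix 1 prevails when they differ.

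**The concern.** Both texts govern one decision, whether nivolumab is held or ended, and they use the same two outer limits (8 x ULN and 5 x ULN). They should therefore be mirror images. They are not, for two reasons.

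- Table 3 has a third, concurrent trigger at lower values, which the footnote does not mention.
- Table 3 joins its triggers with *or*. The opposite of stopping when either limit is exceeded is delaying only when both limits are respected, which needs *and*. The footnote has *or*.

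Two sites could therefore take opposite actions on the same serious liver event, each citing the protocol. The concurrent pattern deserves particular care because its AST/ALT and bilirubin thresholds (above 3 x and above 2 x ULN) are those that Section 11.3.5 uses in defining potential drug-induced liver injury.

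**Working it through.** No stated figure needs reproducing; this is a check of decision logic.

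**Inputs.** Let A be the higher of AST and ALT and B the total bilirubin, both as multiples of ULN at the same time point.

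- Table 3, permanent stop: (A > 8) or (B > 5) or (A > 3 and B > 2).
- Appendix 1 footnote read literally, delay permitted: (A ≤ 8) or (B ≤ 5).
- Appendix 1 footnote read analyte by analyte, so that each value must be within its own limit: (A ≤ 8) and (B ≤ 5).

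**Grid.** Three bands of A (≤ 3, > 3 to 8, > 8) crossed with three bands of B (≤ 2, > 2 to 5, > 5) give nine combinations. Six meet a Table 3 trigger:

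| A (x ULN) | B (x ULN) | Table 3 | Footnote, literal *or* | Footnote, analyte by analyte |
|---|---|---|---|---|
| ≤ 3 | > 5 | stop | delay permitted | delay not permitted |
| > 3 to 8 | > 2 to 5 | stop | delay permitted | delay permitted |
| > 3 to 8 | > 5 | stop | delay permitted | delay not permitted |
| > 8 | ≤ 2 | stop | delay permitted | delay not permitted |
| > 8 | > 2 to 5 | stop | delay permitted | delay not permitted |
| > 8 | > 5 | stop | delay not permitted | delay not permitted |

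**Result.** On the literal reading the texts conflict in 5 of 6 combinations; the exception is both values above their outer limits. On the analyte-by-analyte reading they conflict in 1 of 6.

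**Worked cases (A, B).**

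- 4, 2.5: the concurrent trigger is met because 4 > 3 and 2.5 > 2, so Table 3 stops. Both footnote readings permit delay because 4 ≤ 8 and 2.5 ≤ 5.
- 12, 1: Table 3 stops because 12 > 8. The footnote permits delay only on the literal reading, through 1 ≤ 5.
- 4, 6: Table 3 stops because 6 > 5. The footnote permits delay only on the literal reading, through 4 ≤ 8.
- 10, 6: Table 3 stops, and neither footnote reading permits delay.

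The conflict that survives both readings is the band A > 3 to 8 with B > 2 to 5.

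**The case against.** **The documents' structure favours Table 3.** It is introduced with *must*. Appendix 1 is general guidance for a whole drug class, reached through a section on suggested supportive care, and its footnote says *may*. An investigator who follows Table 3 breaches nothing in the Appendix. This stands and lessens the conflict. It does not settle it: Table 3's own title calls its contents guidelines, the cross-references lead to both texts, and precedence is never stated. Nor are Appendix footnotes confined to supportive care. The skin footnote also addresses discontinuation, and it matches Table 3 on suspected versus confirmed Stevens-Johnson syndrome or toxic epidermal necrolysis.

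**The *or* may be loose drafting.** The outer limits are identical to Table 3's, which suggests that the texts were meant to agree. Read literally, the 8 x ULN limit would do no work for an isolated transaminase rise. This is a fair reading, and it removes four of the five conflicts. It leaves the concurrent trigger.

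**The figure is missing.** The asterisk belongs to an algorithm figure that is not shown, and the box it qualifies might limit which grades the footnote covers. This stands as a caveat. The visible footnote text states no such limit.

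**Stronger inferences a reader might draw.**

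- That the footnote re-exposes subjects. A delay is not a restart: Table 3's hold row for hepatitis requires recovery to Grade 0-1 first. The footnote leaves re-exposure open and does not direct it.
- That the 4, 2.5 case is drug-induced liver injury by the protocol's definition. Section 11.3.5 also requires no initial cholestasis and no other immediately apparent cause.
- That a safety endpoint is compromised. Section 12.5 tabulates proportions of subjects by adverse-event grade; discontinuation for hepatotoxicity is not a named measure there, although Section 6 has events leading to discontinuation assessed at visits.

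**Conclusion.** The two texts conflict, and they need to be reconciled. The firm part is the omitted concurrent trigger: on any reading of the footnote's visible text, values such as ALT 4 x ULN with bilirubin 2.5 x ULN fall under permanent discontinuation in Table 3 and permitted delay in Appendix 1. The wider part, five of six trigger combinations, depends on taking the footnote's *or* literally.

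A reader might infer that nearly every subject who meets a Table 3 trigger would be caught between the two rules. The documents do not support that. They give no distribution of liver values, and the six combinations are categories, not equally likely groups of subjects.

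The conclusion assumes that the unseen figure does not restrict the footnote in a way that removes the overlap. It does not depend on the sample size. The primary response endpoint and the planned adverse-event grade analysis are not affected. What is at stake is uniform handling of a serious liver event across sites. No view is taken here on which clinical rule is right.

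**What to change.** Reconcile the Table 3 hepatitis rows with the Appendix 1 hepatic footnote:

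1. State in Section 6.3.2, and again in Appendix 1, which text governs nivolumab delay and discontinuation in this trial.
2. Make the footnote's connective, and its handling of a concurrent AST/ALT and bilirubin rise, give the same action as the governing text. The algorithms are also in the nivolumab Investigator's Brochure and carry their own update date, so if the Appendix is standard supplier text that cannot be edited, a precedence sentence is enough.
3. When doing so, check the full algorithm figure to confirm which box the asterisk qualifies.

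The sponsor decides which clinical rule applies. The cost is a short clarification in an amendment or memo, with no added procedure, visit or data item.
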